3.3.6 Vital signs

Vital signs data (blood pressure, pulse and temperature) will be obtained at every visit up until treatment discontinuation and will be used for reporting. Change from baseline in vital signs variables will be calculated for each post-dose visit on treatment. For derivation of post-baseline

visit values, considering visit window, and to handle multiple records, derivation rules as described in [Section 3.3.1](#) will be used.

3.3.7 Physical Examinations

Physical examination data (indication whether data were collected or not) will be obtained at the start of each cycle (including screening) up until treatment discontinuation. Clinically significant findings at screening will be recorded in surgical or medical history. Any new or aggravated clinically relevant abnormal medical finding at a physical examination will be reported as an AE.

3.3.8 Electrocardiograms

Electrocardiogram (ECG) data (details of rhythm, ECG intervals and an overall evaluation) will be obtained at every visit until treatment discontinuation. If there is an abnormal on-treatment assessment at the time of treatment discontinuation then a 28-day follow-up assessment will be required to confirm reversibility of the abnormality.

3.3.9 Left ventricular ejection fraction (LVEF)

An echocardiogram or multigated acquisition scan (MUGA) to assess LVEF will be performed at screening (prior to first dose of osimertinib) and at least every 16 weeks throughout the treatment period until patients have reached 3.5 years on the study. Thereafter, echocardiogram or MUGA will be performed at least every 20 weeks for the remainder of the treatment period. Additional assessments of LVEF should be performed as clinically indicated. A 28-day follow-up assessment will be required if an on-treatment assessment was abnormal at the time of discontinuation of study therapy, to confirm reversibility of the abnormality.

3.3.10 Ophthalmological assessments

Full ophthalmic assessment, including slit lamp examination, will be performed if a patient experiences any visual symptoms (including blurring of vision). Ophthalmology examination results should be collected in the eCRF.

Any clinically significant findings, including those confirmed by the ophthalmologist must be reported as an AE.

3.4 Biomarker variables

If a patient progresses in the ELIOS study and then enrols in a subsequent AZ study, and if appropriate consent is provided, the biomarker results from a progression biopsy (generated in

either the other study or ELIOS), may be shared between both studies and the data may be analysed as part of the ELIOS study.

Biological samples, other than those collected for the primary objective, will be collected and may be analysed for **CCI**

4. ANALYSIS METHODS

4.1 General principles

The following general principles will be followed throughout the study:

- Continuous variables will be summarised by the number of observations, mean, standard deviation, median, 1st and 3rd quartiles (where applicable), minimum, and maximum. Categorical variables will be summarised by frequency counts and percentages for each category.
- The minimum and maximum will be reported to the same number of decimal places as the raw data recorded in the database. The mean and median will be reported to one more decimal place, and the standard deviation will be reported to two more decimal places, than the raw data recorded in the database. For laboratory data the recommended number of decimal places per parameter will be used rather than raw data precision.
- Percentages will be presented to one decimal place.
- SAS[®] version 9.3 or later will be used for all analyses.

Study Day 1 is defined as the date of first dose of study drug. For visits (or events) that occur on or after first dose, study day is defined as (date of visit [event] - date of first dose of study drug + 1). For visits (or events) that occur prior to first dose, study day is defined as (date of visit [event] - date of first dose of study drug). There is no Study Day 0.

For safety endpoints the last observation before the first dose of study drug will be considered the baseline measurement unless otherwise specified.

In all summaries change from baseline variables will be calculated as the post-treatment value minus the value at baseline. The percentage change from baseline will be calculated as (post-baseline value - baseline value) / baseline value ×100.

The primary analysis will be based on the PAS. All secondary efficacy, safety, study population and demography data will be summarised and analysed based on the FAS.

The final analysis timepoint, at study end, and when approximately 50 patients have evaluable paired biopsies upon progression, will include production of all the tables, listings and figures, which will be specified and finalised in a separate TLF shell document before database lock.

4.2 Analysis methods

4.2.1 Patient disposition

The total number of patients screened (including screening failures), enrolled (ie, patients with informed consent), patients who received any study drug and patients who did not receive any study drug, patients ongoing treatment at DCO, patients ongoing in the study at DCO, patients who completed treatment, patients who discontinued treatment and the reason for discontinuation, and patients who discontinued the study and the reason for discontinuation will be summarised.

The number and percentage of patients included in the analysis populations and the number of patients recruited by country and centre will be also presented.

4.2.2 Attrition of biopsy samples

To explore why patients who had an evaluable baseline did not have a paired progression sample for the primary analysis, the total number of patients that had a baseline biopsy, the number of patients that had a baseline biopsy that was not evaluable, and the number of patients that had an evaluable baseline biopsy will be summarised. The number of patients that had not progressed at DCO, withdrew from the study prior to progression, died prior to progression, did not have a biopsy after progression, had a progression biopsy that was not evaluable, or had an evaluable progression biopsy will be further summarised for patients that had an evaluable baseline biopsy.

4.2.3 Protocol deviations

All identified important protocol deviations will be listed and summarised for the FAS. All protocol deviations will be defined by the study team and identified and classified as important or not important before database lock. All important protocol deviations confirmed to be due to Coronavirus Disease 2019 (COVID-19) will be summarised.

4.2.4 Demographics and other baseline characteristics

Demographic and baseline subject characteristics will be listed and summarised for the FAS and the PAS and defined subgroups by mutation status. Standard descriptive statistics will be presented for the continuous variables of:

- Age (years)
- Weight (kg)
- Height (cm)
- Body mass index (kg/m²), calculated as: $\frac{weight}{height^2}$
- Nicotine consumption (number of pack years)

The total counts and percentages of patients will be presented for the categorical variables of:

- Age group (years) (grouped as <50, ≥ 50 -<65, ≥ 65 -<75, ≥ 75)
- Sex
- Race
- Ethnic group
- Smoking status.
- WHO performance status (0/1)
- EGFR mutation type (Ex19del, L858R)

4.2.5 Medical history

Relevant medical history (past and current) and relevant surgical history will be coded using the most recent version of MedDRA.

All medical history will be summarised (number and percentage of patients) for the FAS by system organ class (SOC) and preferred term (PT).

4.2.6 Disease history

The following disease characteristics will be summarized for all patients in the FAS (unless specified otherwise), the PAS and defined subgroups by mutation status:

- Disease characteristics at baseline (time from original diagnosis, primary tumour location, histology type, regional lymph nodes, distant metastases, stage/ American Joint Committee on Cancer [AJCC] stage).
- Extent of disease upon entry to study (metastatic/locally advanced, site of metastatic disease).
- Previous cancer therapy (Neo-adjuvant, adjuvant chemotherapy, any previous radiotherapy, any previous surgery).

- EGFR mutation status
- Site of local/metastatic disease
- Brain metastases and Visceral metastases
- Baseline TL size (mean and categories: <40, 40-79, 80-119, \geq 120mm)
- Histology type

4.2.7 Concomitant medication

Prior and concomitant medications are defined as follows:

- Prior medications are medications taken prior to or during screening with a stop date prior to the first dose of study drug
- Concomitant medications are medications with or without a stop date on or after the date of first dose of study drug (and could have started prior to or during treatment).

Concomitant medication will be summarised using frequency tables by Anatomical therapeutic chemical (ATC) classification code (based on World Health Organisation (WHO) classification).

4.2.8 Exposure

The following summaries will be produced for the FAS and the PAS:

- Total exposure to study treatment,
- Actual exposure to study treatment
- Number of and reasons for dose interruptions
- Number of and reasons for dose reductions
- Time on study – defined as the time in days from the start date of treatment to the date of last study assessment or the date of withdrawal.

4.2.9 Primary and Efficacy Endpoints

[Table 9](#) presents the formal statistical analyses to be conducted for the primary and efficacy endpoints.

Table 9 Formal analyses

Endpoints analysed	Notes
Proportion of patients with a given genetic and proteomic marker at the point of disease progression as defined by the Investigator	Primary analysis
PFS	Secondary analysis
Objective response rate	

Duration of response

Disease control rate

Subgroup analyses

PFS

Objective response rate

Best change in TL tumour size

Time to treatment discontinuation or death

Time to treatment discontinuation or death

Time to first subsequent therapy or death

4.2.9.1 Proportion of patients with a given marker

The proportion of patients with a given genetic and proteomic marker at the point of disease progression (as defined by the investigator) will be calculated and presented alongside the associated exact binomial 95% Clopper-Pearson (exact) confidence intervals (CIs).

If a reasonable proportion (at least 20%) of patients have a given marker at baseline, the difference in the proportion of patients with that marker between progression and baseline, together with its 95% adjusted Wald CI, may also be calculated.

The primary analysis table will include the frequency and proportion of new pathogenic, likely pathogenic or ambiguous mutations and will be split by gene name and variant-type. Other tables will follow the same layout but will look at pathogenic, likely pathogenic or ambiguous mutations at baseline and all pathogenic mutations at disease progression. New markers will be defined (for an individual patient) to be those present at progression that were not present at baseline. Only markers defined as 'Pathogenic', 'Likely pathogenic' or 'Ambiguous' by the analysing lab will be tabulated.

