3.1 Inclusion Criteria

For inclusion in the study patients should fulfil the following criteria:

1. Provision of informed consent prior to any study specific procedures (signed and dated Informed Consent Form).
2. Patients aged 18 years or older (specific age may vary according to country regulations for legal age).

3. Patients with histological confirmation of locally advanced or metastatic, non-squamous NSCLC who are not candidates for local curative treatment.
4. Patients with M1 stage according to the Tumour, Node, and Metastasis Classification of Malignant Tumours (TNM) version 7 including M1a (malignant effusion) or M1b (distant metastasis), or locally advanced disease that is not a candidate for curative treatment (including patients who progress after chemo-radiotherapy in stage III disease).
5. Patients with an EGFR deletion or mutation known (from tumour biopsy or plasma) to be associated with EGFR TKI sensitivity before treatment assessed by a local laboratory certified by Clinical Laboratory Improvement Amendments (USA sites) or an accredited local laboratory (sites outside of the USA).
6. Existence of measurable or evaluable disease (as per RECIST 1.1 criteria).
7. Possibility of obtaining sufficient tissue sample, via a biopsy or surgical resection of the primary tumour or metastatic tumour tissue, within the 60 days prior to study entry and at or after RECIST 1.1-defined progression. An archival biopsy is acceptable as long as there has been no intervening anticancer treatment since the time the biopsy was obtained to enrolment in this clinical study and as long as it was within 60 days of study entry. A sufficient tissue sample would consist of formalin-fixed, paraffin-embedded tumour tissue blocks, or at least 15 re-cut unstained sections from formalin-fixed paraffin-embedded tumour tissue block, presented on slides. Each section should be 5 μm thick.
8. WHO performance status 0-1.
9. Life expectancy \geq 12 weeks.
10. Capacity to swallow.
11. Patients able to complete study and within geographical proximity allowing for adequate follow-up.
12. Resolution of all acute toxic effects of previous anticancer therapy (which can only be adjuvant or neoadjuvant) or surgical interventions to Grade 1 according to the National Cancer Institute (NCI) CTCAE version 4.0 (except for alopecia or other side effects that the Investigator does not consider to be a risk to patient safety).

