8.4 Outcome Measures for Analyses

8.4.1 Calculation or derivation of primary endpoint variables

The primary endpoint is the proportion of patients with a given genetic and proteomic marker (including, but not limited to, EGFR mutations, HER2, and cMET expression and/or amplification) at the point of disease progression as defined by the Investigator; the choice of markers is dependent on the profile comparison at the point of disease progression and prior to treatment initiation. The number of patients with a given genetic and proteomic marker will be divided by the number of patients who have evaluable biopsies and have progressed according to the Investigator to calculate the proportion with a given marker at progression.

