1.3 Number of Patients

It has been determined that approximately 150 patients are appropriate to characterize the frequency of tumour genetic and proteomic markers at disease progression regardless of their prevalence. [Table 2](#) displays the precision of the estimated frequency of mutation when, for example, 50 evaluable paired biopsies are available.

The final analysis will be performed at study end, and when approximately 50 patients have evaluable paired biopsies upon progression. Assuming a 70% of rate of patients having a biopsy at both baseline and progression, and with an assumed technical failure rate of 30% of the samples (assume an overall failure rate of 51%), then we should expect approximately 50 evaluable paired biopsies to be available when approximately 103 of the 150 patients have progressed, which would be expected to occur approximately 38 months after the first patient is enrolled. This calculation assumes patients are recruited over 12 months, exponentially distributed progression times with a 19-month median and a 2-piece recruitment function that assumes an exponentially distributed recruitment rate.

Table 2 Precision of Estimates of Marker Frequency with 50 Available and Evaluable Paired Biopsies

Marker Frequency	95% confidence interval ^a
10%	(3%, 22%)
30%	(18%, 45%)
50%	(36%, 64%)

^a Exact binomial confidence intervals.

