2.1.2 Full analysis set

The (FAS) will include all patients who receive at least one dose of osimertinib. The FAS will be used for all efficacy and safety analyses.

[Table 3](#) summarises the population analysis sets for each outcome variable.

Table 3 Summary of outcome variables and analysis populations

Outcome variable	Population
Primary objective	
Proportion of patients with a given marker at progression as defined by the investigator	PAS
Efficacy data	
PFS, ORR, DoR, DCR, TTD, TFST	FAS
Subgroup analysis	
PFS, ORR, Best change in TL tumour size, TTD	FAS
Important patient and disease characteristics	FAS, PAS
Demography data	
Important patient and disease characteristics	FAS, PAS
Safety data	
Exposure	FAS
AEs	FAS
Laboratory measurements	FAS
Vital signs	FAS
Physical examinations	FAS
Electrocardiograms (ECGs)	FAS

Abbreviations: AEs = Adverse events; DCR = Disease control rate; DoR = Duration of response; ECG = Electrocardiogram; FAS = Full analysis set; ORR = Objective response rate; PAS = Primary analysis set; PFS = Progression free survival; TFST = Time to first subsequent therapy or death; TL = Target lesion; TTD = Time to treatment discontinuation or death.

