3.2 Efficacy variables

3.2.1 Primary endpoint

The primary endpoint is the proportion of patients with a given genetic and proteomic marker (including, but not limited to, EGFR mutations, HER2, and cMET expression and/or amplification) at the point of RECIST disease progression as defined by the Investigator; the choice of markers is dependent on the profile comparison at the point of disease progression and prior to treatment initiation. The number of patients with a given genetic and proteomic marker will be divided by the number of patients who have evaluable paired biopsies and have progressed according to the Investigator to calculate the proportion with a given marker at progression. New markers will be defined (for an individual patient) to be those present at progression that were not present at baseline. Only markers defined as 'Pathogenic', 'Likely pathogenic' or 'Ambiguous' by the analysing lab will be tabulated.

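### SAP 4.2.9.1 puts the primary label on a table of newly gained mutations, while the stated primary endpoint is the proportion of patients with the marker at progression

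*SAP*

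**What the plan says.** **Where the endpoint is the marker at progression.** SAP 3.2.1 divides the patients with a marker by those with evaluable paired biopsies who have progressed according to the Investigator, "to calculate the proportion with a given marker at progression". Protocol 8.4.1 uses the same numerator and names the markers as "including, but not limited to, EGFR mutations, HER2, and cMET expression and/or amplification". SAP Table 3 (section 2.1.2) lists the primary objective as "Proportion of patients with a given marker at progression as defined by the investigator". In SAP Table 9 (section 4.2.9) the row marked as the primary analysis reads "Proportion of patients with a given genetic and proteomic marker at the point of disease progression as defined by the Investigator". The opening sentence of SAP 4.2.9.1 plans that proportion with a Clopper-Pearson 95% CI. SAP 1.3 calls the sample size "appropriate to characterize the frequency of tumour genetic and proteomic markers at disease progression regardless of their prevalence".

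**Where it is new mutations.** The third paragraph of SAP 4.2.9.1 says "The primary analysis table will include the frequency and proportion of new pathogenic, likely pathogenic or ambiguous mutations". A new marker is one that an individual patient has at progression and did not have at baseline. SAP 3.2.1 gives the same definition of new markers, but does not make them the endpoint.

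**Call classes.** SAP 4.2.9.1 names pathogenic, likely pathogenic and ambiguous calls for the new-mutation and baseline tables. For the progression table it says "all pathogenic mutations at disease progression". Its closing sentence limits all tabulation to the three classes.

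**Changes from protocol.** SAP section 6 states only which protocol version was used.

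**The concern.** The word 'primary' is attached to two different numerators within one SAP. A programmer or report author who follows Table 9 will headline one percentage, and one who follows the third paragraph of 4.2.9.1 will headline another. A reader of the study report who sees a table called primary will take its percentages as the protocol endpoint. They are not, for any marker that some patients carry at both timepoints.

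The class wording compounds this. New mutations are by definition a subset of mutations at progression. If the subset is tabulated over three classes and the whole over one, the subset can come out larger than the whole, and the result that matches the endpoint is the one understated.

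**Working it through.** **The plan's own figures.** SAP Table 2 gives exact 95% intervals for 50 pairs. Clopper-Pearson limits reproduce it: 5/50 gives 3.3 to 21.8%, 15/50 gives 17.9 to 44.6%, and 25/50 gives 35.5 to 64.5%. The printed values are (3, 22), (18, 45) and (36, 64), which agree after rounding of the unrounded limits. The table is therefore sound as the precision of a single proportion, and SAP 1.3 presents it for markers at progression.

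**Relation between the two proportions.** Among n paired patients let P carry the marker at both timepoints (persisting) and let G gain it.
- At progression (the stated endpoint): (P + G)/n
- New (the table called primary): G/n
- Gap: P/n

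The gap is zero only if nobody carries the marker at both timepoints, for example when it is absent at baseline.

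The documents give n = 50 as their example. All marker counts below are assumed for illustration.

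**Example 1, an ordinary marker.** P = 4, G = 9.
- At progression: 13/50 = 26% (14.6 to 40.3)
- New: 9/50 = 18% (8.6 to 31.4)
- Gap: 4/50 = 8 points

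**Example 2, the sensitising EGFR alteration.** Inclusion criterion 5 (protocol 3.1) admits "Patients with an EGFR deletion or mutation known (from tumour biopsy or plasma) to be associated with EGFR TKI sensitivity before treatment". Take it as present at baseline in all 50. This is an upper bound, because eligibility rested on local tests of tumour or plasma. No patient can then gain it, so new = 0/50 = 0% (0 to 7.1).

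| Assumed persistence | At progression | New |
|---|---|---|
| 80% | 40/50 = 80% (66.3 to 90.0) | 0% |
| 90% | 45/50 = 90% (78.2 to 96.7) | 0% |
| 100% | 50/50 = 100% (92.9 to 100) | 0% |

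**Example 3, the class wording read literally.** An amplification is absent at baseline and gained by 8 patients, of whom 5 have pathogenic calls and 3 have likely pathogenic or ambiguous calls.
- New, three classes: 8/50 = 16% (7.2 to 29.1)
- At progression, pathogenic only: 5/50 = 10% (3.3 to 21.8)
- At progression, three classes: 8/50 = 16%, equal to new as it should be

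**Minor detail, the interval for the optional difference.** SAP 4.2.9.1 allows an adjusted Wald CI for progression minus baseline when at least 20% have the marker at baseline, but does not name the form. Assume 8 persist, 4 are lost, 9 are gained and 29 have it at neither time. Baseline is 12/50 = 24%, progression is 17/50 = 34%, and the difference is +10 points. The matched-pair form (Agresti-Min, 0.5 added per cell, N = 52) has centre (9.5 − 4.5)/52 = 9.6 points and half-width 1.96 × √(14 − 25/52)/52 = 13.9 points, giving −4.2 to 23.5. The independent-sample form (Agresti-Caffo) would give −7.9 to 27.1.

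**The case against.** **No analysis is missing.** This stands. A reader might infer that the protocol endpoint has been dropped. It has not: the first sentence of SAP 4.2.9.1 plans it with its exact CI, and a progression table is listed. The disputed phrase names an output table, and the table shells are in a separate document.

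**New markers belong to the primary question.** This stands in part. The objective compares progression with baseline, and SAP 3.2.1 defines new markers under the primary endpoint heading. Showing them prominently is sensible. But the clause on choice of markers governs which markers are reported. The numerator is fixed separately, and it is the marker at progression.

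**The EGFR contrast is a special case.** This stands. A reader might infer that new EGFR mutations will be near zero in general. Only the sensitising alteration required at entry behaves that way. Another EGFR mutation can be gained during treatment, and the table is split by gene and variant type, so it would appear as new.

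**The class wording is an editing slip.** This is probably right. The closing sentence of 4.2.9.1 points to three classes throughout, and the SAP amendment history dates the ambiguous class to May 2023. The documents do not show that likely pathogenic and ambiguous calls will in fact be excluded at progression. They do show two instructions that conflict.

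**Counting unit and paired interval.** A reader might infer that mutations will be counted instead of patients, or that an unpaired interval will be used. No text says either; the section title and the per-patient definition of new markers point to patient counts. These are missing details.

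**The study is exploratory.** This is true. No test or success threshold hangs on the label, which limits the harm to misreporting of the headline result.

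**Conclusion.** The mismatch is in the text and should be fixed. The stated endpoint is the marker at progression, and the table called primary holds gained mutations only. It is a misplaced label on a planned analysis. SAP section 6 is silent on it; that silence is neither a declaration that nothing changed nor evidence of a deliberate change of endpoint.

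The size for any marker is the persisting share P/n. It cannot be stated in advance, because the documents give no baseline or persistence frequencies. It is 8 points in the assumed ordinary example, 80 to 100 points in the upper-bound example for the sensitising alteration, and zero for markers absent at baseline, provided the call classes match. The class wording is a second, smaller conflict that affects results only if followed literally. Confidence is high on the textual mismatch; the percentages are illustrations.

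**What to change.** In SAP 4.2.9.1:

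1. Make the primary analysis table the proportion of patients with each marker at progression, with its Clopper-Pearson 95% CI, and keep baseline and new (gained) counts as columns beside it. If the sponsor intends new mutations to be primary, align SAP 3.2.1, Table 3 and Table 9 instead, reconcile this with protocol 8.4.1, and record the change in SAP section 6.
2. For the progression table, replace the pathogenic-only wording with all pathogenic, likely pathogenic or ambiguous mutations at disease progression.
3. As minor clarifications, state that each patient counts once per row, as SAP 4.2.10.1 already does for adverse events, and name the matched-pair form of the adjusted Wald interval wherever the optional difference is calculated. The 20% condition can stay.

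The cost is SAP wording and extra columns in planned tables. No new data are needed. Under the main option no protocol amendment is needed either, because the table returns to the protocol endpoint. The downside is wider tables.
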